Starting on Cycle 1, Day 1, eligible patients will receive AL101, either 4 mg QW IV in Cohort 1 or 6 mg QW IV in Cohort 2, on Days 1, 8, 15, and 22 of each 28-day cycle until disease progression, unacceptable toxicity, or consent withdrawal. For patients with radiological progression, investigational product may be continued as long as the patient is having clinical benefit, is agreed to by the patient and physician and approved by the Sponsor's Medical Monitor.

Paired tumor biopsies will be collected at screening (fresh or archival within 3 years) and on-treatment at Cycle 4 Day 1 ±28 days provided medically safe and not contraindicated. Samples will be sent to a central vendor for NGS analysis. Tumor Formalin-fixed paraffin embedded

 If an archival tumor block or 25 unstained slides are not available, the patient will be required to have a fresh tumor sample obtained at screening.

(FFPE) slides will be evaluated by IHC for NICD1 stain. On the day of the on-treatment biopsy, blood will also be drawn for PK and biomarker assessments.

During the Treatment period, patients will undergo radiographic assessments every 8 weeks ( $\pm 3$  days) for review by the Investigator. Scans will be collected and held for possible future retrospective evaluation by ICR. Other assessments will be done as specified in Schedule of Activities (SoA; [Table 1](#)), including safety and exploratory biomarkers.

A repeat of tumor imaging will be required for the purposes of confirmation of response (i.e., partial response, and/or complete response). The confirmation scan should be no earlier than 4 weeks following the first indication of response.

All patients will undergo end of study (EOS) visit 30 days post last treatment and be contacted by phone every 3 months to determine survival status. In patients who discontinued investigational product due to toxicity, radiographic imaging will be done every 3 months until disease progression or until patient initiates another anti-cancer therapy.

Study participation for each patient consists of:

Screening period: up to 28 days

Treatment period: Weekly treatment, until disease progression, unacceptable toxicity, or consent withdrawal

EOS: 30 days after the last administration of investigational product.

Long term follow-up: Every 3 months.

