#### 4.5 EARLY WITHDRAWAL OF PATIENTS FROM THERAPY OR ASSESSMENT

Patients are free to discontinue their participation in the study at any time and without prejudice to further treatment. The Investigator must withdraw any patient from the study if that patient requests to be withdrawn, or if it is determined that continuing in the study would result in a significant safety risk to the patient.

Discontinuation or interruption of investigational product does not represent withdrawal from the study. Patients may withdraw or be withdrawn from investigational product at any time.

Patients who permanently discontinue investigational product or are withdrawn from the study for non-safety reasons prior to the first efficacy endpoint (i.e., upon 2 cycles of treatment) may be replaced.

Dosing of investigational product must be interrupted for any serious adverse reactions assessed by the investigator as related to investigational product. Restart of dosing may be considered upon approval by the Sponsor's Medical Monitor (or designee) after resolution of IP treatment-related events to baseline.

Please refer to Section [6.6](#) for AL101 dose modifications and toxicity management which may lead to investigational product discontinuation. Pregnancy is a mandatory criterion for permanent discontinuation of investigational product. Any patient being managed with dose interruption for toxicity should have their study assessments followed per SoA.

The patient's participation in the study may be discontinued due to the following reasons:

- Request of Investigator
- Life-threatening event or death
- Patient withdrew consent
- Patient is lost-to-follow-up

The patient may discontinue investigational product due to the following reasons:

- Request of the Investigator
- Adverse event
- Treatment failure
- Patient is non-compliant with study procedures or study protocol

Confidential

Document State: Effective (Controlled)  
CONFIDENTIAL

Page 39 of 118

- Request of Sponsor or regulatory authority
- Pregnancy
- Other (to be specified in the electronic case report form; eCRF)

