#### **4.6 HANDLING OF WITHDRAWALS**

If a patient is withdrawn from the study, every effort should be made to determine the reason. This information will be recorded on the patient's eCRF. Patients who withdraw from the study, regardless of cause, should undergo all EOS assessments as specified in Schedule of Activities (SoA; Table 1). Follow-up visits will be scheduled, per protocol.

Patients will be asked to agree to be followed up as stated in the protocol regardless of the reason for discontinuation.

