## **6.6 DOSE MODIFICATION AND TOXICITY MANAGEMENT GUIDELINES**

Dose modification associated with AL101 is described below in [Table 6](#).

The causality assessment system proposed by the World Health Organization Collaborating Centre for International Drug Monitoring, the Uppsala Monitoring Center (WHO-UMC) will be used by the Investigator for assessing drug-related (certain, probable/likely, possible) non-hematological Grade 3 (except isolated Grade 3 electrolyte abnormality that are not associated with clinical signs or symptoms and are reversed with appropriate medical intervention within 48 hours) and hematological Grade 4 toxicities will lead to a 1 dose level reduction for AL101. For easily manageable Grade 1 or 2 toxicity, no dose reductions are required, but careful observation and treatment is required. Dose modification of intolerable Grade 2 toxicity will be evaluated on a case-by-case basis with the Sponsor. Re-escalation of the dose following a dose reduction is allowed only after discussion and approval of the Sponsor's Medical Monitor. Maximum AL101 treatment interruption allowed is 28 days; treatment interruption longer than 28 days will result in discontinuation of patient from the study. Additional treatment guidelines may be implemented by the Investigators, with agreement of the Sponsor/Medical Monitor, as needed to ensure patient safety.

 "The use of the WHO-UMC system for standardized case causality assessment" a communication by WHO-UMC in 2011; [https://www.who-umc.org/media/164200/who-umc-causality-assessment\\_new-logo.pdf](https://www.who-umc.org/media/164200/who-umc-causality-assessment_new-logo.pdf)

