Confidential

 Document State: Effective (Controlled)  
 CONFIDENTIAL

Page 56 of 118

Dose Modification Criteria for AL101 -Related Adverse Events	AL101 modification	
	Note: for any questions, please contact the Sponsor's Medical Monitor.	
	Cohort 1 (4 mg QW IV)	Cohort 2 (6 mg QW IV)
	
Interrupt AL101 until resolution to <math>\leq</math> Grade 1 (refer to Section 6.6.2 and above for management guidelines for diarrhea).
 
Decrease AL101 dose to 2.4 mg QW.
 
If the diarrhea does not resolve to Grade 1 by 14 days, the patient will be discontinued from AL101 (refer to Section 4.5 for early withdrawal of patients from therapy or assessment).
 
If treatment interruption is longer than 28 days, the patient will be discontinued from AL101 (refer to Section 4.5 for early withdrawal of patients from therapy or assessment).
	
Interrupt AL101 until resolution to <math>\leq</math> Grade 1 (refer to Section 7.1.2 and above for management guidelines for diarrhea).
 
Change dose regimen to 6 mg 2 weeks on / 1 week off for the first episode.
 
Decrease AL101 dose to 4 mg QW for second episode and to 2.4 mg QW for third episode
 
If the diarrhea does not resolve to Grade 1 by 14 days, the patient will be discontinued from AL101 (refer to Section 4.5 for early withdrawal of patients from therapy or assessment).
 
If treatment interruption is longer than 28 days, the patient will be discontinued from AL101 (refer to Section 4.5 for early withdrawal of patients from therapy or assessment).

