Any other AL101-related Grade 3 nonhematologic adverse event except electrolyte abnormalities that may be managed with supplements	Interrupt AL101 until resolution to $\leq$ Grade 1 and then resume at 1 dose level lower (i.e., 2.4 mg QW). If treatment interruption is longer than 28 days, the patient will be discontinued from the study (refer to Section 4.5 for early withdrawal of patients from therapy or assessment).	Interrupt AL101 until resolution to $\leq$ Grade 1 and then change dose regimen to 6 mg 2 weeks on / 1 week off for the first episode. Decrease dose to 4 mg QW for second episode and to 2.4 mg QW for third episode. If treatment interruption is longer than 28 days, the patient will be discontinued from the study (refer to Section 4.5 for early withdrawal of patients from therapy or assessment).

Confidential

 Document State: Effective (Controlled)  
 CONFIDENTIAL

Page 60 of 118

Dose Modification Criteria for AL101 -Related Adverse Events	AL101 modification	
	Note: for any questions, please contact the Sponsor's Medical Monitor.	
	Cohort 1 (4 mg QW IV)	Cohort 2 (6 mg QW IV)
Grade 4 non-hematologic AEs including Grade 4 non-hematologic lab abnormalities lasting > 72 hours	Permanently discontinue from IP (refer to Section 4.5 for early withdrawal of patients from therapy or assessment ).	Permanently discontinue from IP (refer to Section 4.5 for early withdrawal of patients from therapy or assessment ).

Confidential

 Document State: Effective (Controlled)  
 CONFIDENTIAL

Page 61 of 118

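### After an interruption of more than 28 days, Section 6.6 and seven Table 6 rows discontinue the patient from the study, two rows only from AL101, and Section 4.5 keeps the two apart

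*Protocol*

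**What the plan says.** Protocol Section 6.6 sets 28 days as the longest permitted interruption of AL101 and states that "treatment interruption longer than 28 days will result in discontinuation of patient from the study".

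Table 6 in the same section repeats the rule with two outcomes. Most rows that carry it read "If treatment interruption is longer than 28 days, the patient will be discontinued from the study". The Grade 2 and Grade 3 diarrhea rows read "If treatment interruption is longer than 28 days, the patient will be discontinued from AL101".

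Section 4.5 treats drug and study as separate: "Discontinuation or interruption of investigational product does not represent withdrawal from the study". It describes Section 6.6 as covering "dose modifications and toxicity management which may lead to investigational product discontinuation". Its list of reasons for ending study participation does not include a long interruption.

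On follow-up, Section 3 says: "In patients who discontinued investigational product due to toxicity, radiographic imaging will be done every 3 months until disease progression", or until another anti-cancer therapy starts. Section 4.6 deals with patients who leave the study for any cause. They have the end-of-study (EOS) assessments, and then "Follow-up visits will be scheduled, per protocol". Section 5 continues the 3-monthly survival calls until death, withdrawal of consent or termination by the sponsor.

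**The concern.** The same operational event, an interruption that passes day 28, has two stated outcomes depending on which toxicity caused it. A site coordinator who looks up the relevant row will usually find an instruction to take the patient off the study.

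This matters for three kinds of data:

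- **PFS, DOR and OS.** SAP Section 6.4.1.2 censors PFS and DOR at the last disease assessment and OS at the last date known alive. If a site stops scans or calls too early, censoring moves earlier for a reason tied to toxicity.
- **Response confirmation.** A CR or PR must be confirmed at least 4 weeks later. Under SAP Table 6, a PR followed by a non-evaluable time point becomes SD or NE. A missed confirmation scan can therefore change a patient's classification on the primary endpoint.
- **Disposition.** Protocol Section 9.4 and SAP Section 7.3.1 tabulate treatment discontinuation and study termination separately. Identical interruptions could fall in different tables according to adverse event type.

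**Working it through.** The plan states no figure on this point and no sample size or power depends on it, so the check is a count and a comparison of passages.

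**Step 1: which Table 6 rows carry the 28-day rule.** Table 6 has 19 rows, of which 9 carry it.

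| Table 6 row | Discontinued from (both cohorts) |
|---|---|
| CD4+ T-cell depletion, Grade 3 or higher | the study |
| Grade 2 diarrhea | AL101 |
| Grade 3 diarrhea | AL101 |
| GI bleeding or unexplained hemoglobin drop | the study |
| QTcF above 500 msec | the study |
| AST or ALT above 5 times ULN | the study |
| Persistent Grade 3 triglycerides | the study |
| Infusion reaction, Grade 3 or higher | the study |
| Other Grade 3 nonhematologic event | the study, citing Section 4.5 |

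Seven of 9 rows say the study and 2 of 9 say AL101. With two cohort columns that is 7 × 2 = 14 of 18 cells against 2 × 2 = 4 of 18.

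**Step 2: compare with Section 4.5.** Section 4.5 has no 28-day threshold, so the conflict with it is one of principle: stopping drug is not leaving the study. The last row in the table shows the tension in a single sentence, because it ends study participation and refers the reader to Section 4.5 for how to do so.

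**Step 3: compare with the Grade 4 rows.** Grade 4 diarrhea, Grade 3 or 4 gastric hemorrhage and Grade 4 nonhematologic events lead to discontinuation of AL101 or investigational product. Read literally, a Grade 3 event with a 29-day interruption ends the study for the patient, while a Grade 4 event ends only drug. The two sets of rows need to be reconciled; which treatment rule is right is not a question for this review.

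**Step 4: what happens to follow-up under each reading.**

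| Follow-up | If discontinued from AL101 | If discontinued from the study |
|---|---|---|
| EOS visit, with imaging | Yes (Section 5, Table 1) | Yes (Section 4.6) |
| 3-monthly imaging | Yes, for toxicity (Section 3; Table 1, footnote m) | Not stated directly; Section 4.6 points to per-protocol follow-up, and the patient has in fact stopped drug for toxicity |
| Survival calls | Yes (Section 5) | Yes by Section 5, which does not list this as a reason to stop |

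The protocol's intention is the same in both columns. In the right-hand column, however, the site has to infer it from other sections.

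**Step 5: the SAP.** SAP Table 7 has a row for treatment discontinuation due to toxicity or another reason, censored at the date of the last disease assessment. It does not say whether that means the last assessment up to discontinuation or the last one including 3-monthly follow-up scans. Under the first meaning, those scans do not affect PFS or DOR whatever Section 6.6 says. Under the second, Section 6.6 matters, because it may determine whether the scans are done.

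**The case against.** The strongest reply is that follow-up is already protected. Section 4.6 schedules it after study withdrawal whatever the cause and asks patients to agree to it. Section 5 does not end survival calls for an interruption. Section 11.6 says survival data are collected beyond the 30-day visit. Section 3 triggers 3-monthly imaging by stopping drug for toxicity, which describes these patients. Section 4.5 also signals that Section 6.6 is about drug. On this view, all that is left is loose wording.

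Most of that stands. A reader might infer that the protocol itself removes these patients from PFS and survival follow-up, producing toxicity-linked censoring that is heavier at 6 mg. The documents do not support that. Sections 3, 4.6 and 5 point the other way. For PFS and DOR, SAP Table 7 already censors on toxicity discontinuation, so correcting Section 6.6 alone would not settle the matter. No interruption rate is given for either dose, and the evidence on dose is mixed: Section 1.4.1 reports dose-limiting toxicities at 6 mg and 8.4 mg, while Section 1.3.2 reports broadly similar adverse event frequencies at 4 mg and 6 mg in combination with chemotherapy.

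What the reply does not remove is the contradiction. Sections 4.6 and 5 show what was intended; they do not change the instruction that a site reads in Table 6.

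**Conclusion.** The contradiction is established on the text: Section 6.6 and seven of the nine rows with the rule on one side, two rows and the Section 4.5 principle on the other. Loss of follow-up is a risk of misreading at sites, and the protocol does not prescribe it. Inconsistent disposition coding is a further risk.

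The size cannot be estimated, because the documents report neither how many interruptions exceed 28 days nor how sites have applied the rule. The test of 8% against 25% for ORR, with its sample size and power, is unaffected, although a missed confirmation scan could alter an individual patient's response. The effect on PFS and DOR also depends on the unresolved meaning of the SAP Table 7 row. The point is worth correcting because the remedy is small.

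**What to change.** 1. Reconcile Section 6.6, the nine Table 6 rows and Section 4.5, so that an interruption over 28 days has one stated consequence for study status.
2. Add one sentence: patients whose interruption exceeds 28 days remain in 3-monthly imaging, until progression or a new anti-cancer therapy, and in survival follow-up, unless they withdraw consent.
3. In SAP Table 7, state whether scans after discontinuation for toxicity count for PFS and DOR.
4. If it is too late for a protocol change to affect conduct (the SAP describes an update shortly before database lock), list the patients with interruptions over 28 days. Check that their follow-up was completed, and code their disposition in one way.

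The cost is a wording change in each document, plus a short data review if step 4 applies. The follow-up is already planned, so no new assessment is added. No dosing or treatment-stopping rule is proposed.

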**Table 6 Dose Modification Criteria for AL101**

Dose Modification Criteria for AL101 -Related Adverse Events	AL101 modification	
	Note: for any questions, please contact the Sponsor's Medical Monitor.	
	Cohort 1 (4 mg QW IV)	Cohort 2 (6 mg QW IV)
Grade 4 neutropenia lasting $\geq$ 7 days	Decrease by 1 dose level to 2.4 mg QW.	Decrease dose to 4 mg QW for first episode and to 2.4 mg QW for second episode
Grade 3 febrile neutropenia lasting $>$ 24 hours	Decrease by 1 dose level to 2.4 mg QW.	Decrease dose to 4 mg f QW or first episode and to 2.4 mg QW for second episode.
Grade 4 febrile neutropenia	Discontinue.	Discontinue.
Grade 4 thrombocytopenia or $\geq$ Grade 3 thrombocytopenia with significant bleeding	Decrease by 1 dose level to 2.4 mg QW.	Decrease dose to 4 mg QW for first episode and to 2.4 mg QW for second episode
$\geq$ Grade 3 CD4+ T-cell depletion (counts $<$ 200 cells/ $\mu$ L)	Interrupt AL101 until resolution to Grade 1, then resume at 1 dose level lower (i.e., 2.4 mg QW) . If treatment interruption is longer than 28 days, the patient will be discontinued from the study.	Interrupt AL101 until resolution to Grade 1, then resume at 4 mg QW dose level. For second episode, reduce dose to 2.4 mg QW.  If treatment interruption is longer than 28 days, the patient will be discontinued from the study.
Grade 1 diarrhea	No change in AL101 dose. Guidelines for the management of diarrhea: 
 
• Loperamide 4 mg at the first onset of diarrhea, then 2 mg every 2 hours around-the-clock until diarrhea free for at least 12 hours. Patients may take loperamide 4 mg every 4 hours during the night. These doses should not be used for more than 48 hours due to the risk of paralytic ileus.
 
• For patients that cannot tolerate loperamide or do not get adequate relief with maximum
 
	No change in AL101 dose. Guidelines for the management of diarrhea: 
 
• Loperamide 4 mg at the first onset of diarrhea, then 2 mg every 2 hours around-the-clock until diarrhea free for at least 12 hours. Patients may take loperamide 4 mg every 4 hours during the night. These doses should not be used for more than 48 hours due to the risk of paralytic ileus.
 
• For patients that cannot tolerate loperamide or do not get adequate relief with maximum doses, standard doses of LOMOTIL®
 

Confidential

 Document State: Effective (Controlled)  
 CONFIDENTIAL

Dose Modification Criteria for AL101 -Related Adverse Events	AL101 modification	
	Note: for any questions, please contact the Sponsor's Medical Monitor.	
	Cohort 1 (4 mg QW IV)	Cohort 2 (6 mg QW IV)
	
doses, standard doses of LOMOTIL® (diphenoxylate/atropine) may be added or used instead of loperamide.
 
Additional antidiarrheal measures, such as octreotide, may be used at the discretion of the investigator or treating physician.
	
(diphenoxylate/atropine) may be added or used instead of loperamide.
 
Additional antidiarrheal measures, such as octreotide, may be used at the discretion of the investigator or treating physician.

Grade 2 diarrhea	
Guidelines for the management of diarrhea:
 
 
Evaluate patient carefully including laboratory assessments (chemistry, liver function tests and lipase)
 
Loperamide 4 mg at the first onset of diarrhea, then 2 mg every 2 hours around-the-clock until diarrhea free for at least 12 hours. Patients may take loperamide 4 mg every 4 hours during the night. These doses should not be used for more than 48 hours due to the risk of paralytic ileus.
 
For patients that cannot tolerate loperamide or do not get adequate relief with maximum doses, standard doses of LOMOTIL® (diphenoxylate/atropine) may be added or used instead of loperamide.
 
Additional antidiarrheal measures, such as octreotide, may be used at the discretion of the investigator or treating physician
 
 
If the above measures have not worked, or patient has progressed to Grade 2, or after Grade 1 with no
	
Guidelines for the management of diarrhea:
 
 
Evaluate patient carefully including laboratory assessments (chemistry, liver function tests and lipase)
 
Loperamide 4 mg at the first onset of diarrhea, then 2 mg every 2 hours around-the-clock until diarrhea free for at least 12 hours. Patients may take loperamide 4 mg every 4 hours during the night. These doses should not be used for more than 48 hours due to the risk of paralytic ileus.
 
For patients that cannot tolerate loperamide or do not get adequate relief with maximum doses, standard doses of LOMOTIL® (diphenoxylate/atropine) may be added or used instead of loperamide.
 
Additional antidiarrheal measures, such as octreotide, may be used at the discretion of the investigator or treating physician
 
 
If the above measures have not worked, or patient has progressed to Grade 2, or after Grade 1 with no

Confidential

 Document State: Effective (Controlled)  
 CONFIDENTIAL

Dose Modification Criteria for AL101 -Related Adverse Events	AL101 modification	
	Note: for any questions, please contact the Sponsor's Medical Monitor.	
	Cohort 1 (4 mg QW IV)	Cohort 2 (6 mg QW IV)
	
improvement within 3 days with maximum doses of loperamide:
 
 
• Patient may be treated with dexamethasone at a dose of 8 mg every 8 hours (Q8h) for up to 5 days. If still no improvement in symptoms, the patient may continue with the dexamethasone or consider switching to budesonide 9 mg once daily (QD). Refer to Section 7.1.2 for additional instructions on premedication with steroids.
 
 
Dose modifications for AL101:
 
Interrupt AL101 until resolution to <math>\leq</math> Grade 1 (refer to Section 7.1.2 for management guidelines for diarrhea and above for management guidelines for diarrhea).
 
Decrease AL101 dose to 2.4 mg QW.
 
If the diarrhea does not resolve to Grade 1 by 14 days, the patient will be discontinued from AL101 (refer to Section 4.5 for early withdrawal of patients from therapy or assessment).
 
If treatment interruption is longer than 28 days, the patient will be discontinued from AL101 (refer to Section 4.5 for early withdrawal of patients from therapy or assessment).
	
improvement within 3 days with maximum doses of loperamide:
 
 
• Patient may be treated with dexamethasone at a dose of 8 mg Q8h for up to 5 days. If still no improvement in symptoms, the patient may continue with the dexamethasone or consider switching to budesonide 9 mg QD. Refer to Section 7.1.2 for additional instructions on premedication with steroids.
 
 
Dose modifications for AL101:
 
Interrupt AL101 until resolution to <math>\leq</math> Grade 1 (refer to Section 7.1.2 and above for management guidelines for diarrhea).
 
Change dose regimen to 6 mg 2 weeks on / 1 week off for first episode
 
Decrease AL101 dose to 4 mg QW for second episode and to 2.4 mg QW for third episode.
 
If the diarrhea does not resolve to Grade 1 by 14 days, the patient will be discontinued from AL101 (refer to Section 4.5 for early withdrawal of patients from therapy or assessment).
 
If treatment interruption is longer than 28 days, the patient will be discontinued from AL101 (refer to Section 4.5 for early withdrawal of patients from therapy or assessment).

Grade 3 diarrhea	Guidelines for the management of diarrhea:	Guidelines for the management of diarrhea:

Confidential

 Document State: Effective (Controlled)  
 CONFIDENTIAL

Page 55 of 118

Dose Modification Criteria for AL101 -Related Adverse Events	AL101 modification Note: for any questions, please contact the Sponsor's Medical Monitor.	
	Cohort 1 (4 mg QW IV)	Cohort 2 (6 mg QW IV)
	
 
Evaluate patient carefully including laboratory assessments (chemistry, liver function tests and lipase)
 
Loperamide 4 mg at the first onset of diarrhea, then 2 mg every 2 hours around-the-clock until diarrhea free for at least 12 hours. Patients may take loperamide 4 mg every 4 hours during the night. These doses should not be used for more than 48 hours due to the risk of paralytic ileus.
 
For patients that cannot tolerate loperamide or do not get adequate relief with maximum doses, standard doses of LOMOTIL® (diphenoxylate/atropine) may be added or used instead of loperamide.
 
Additional antidiarrheal measures, such as octreotide, may be used at the discretion of the investigator or treating physician
 
 
If the above measures have not worked, or patient has progressed to Grade 3:
 
 
Treat with dexamethasone at a dose of 8 mg Q8h for up to 5 days. If still no improvement in symptoms, the patient may continue with the dexamethasone or consider switching to budesonide 9 mg QD. Refer to Section 7.1.2 for additional instructions on premedication with steroids.
 
 
Dose modifications for AL101:
	
 
Evaluate patient carefully including laboratory assessments (chemistry, liver function tests and lipase)
 
Loperamide 4 mg at the first onset of diarrhea, then 2 mg every 2 hours around-the-clock until diarrhea free for at least 12 hours. Patients may take loperamide 4 mg every 4 hours during the night. These doses should not be used for more than 48 hours due to the risk of paralytic ileus.
 
For patients that cannot tolerate loperamide or do not get adequate relief with maximum doses, standard doses of LOMOTIL® (diphenoxylate/atropine) may be added or used instead of loperamide.
 
Additional antidiarrheal measures, such as octreotide, may be used at the discretion of the investigator or treating physician
 
 
If the above measures have not worked, or patient has progressed to Grade 3:
 
 
Treat with dexamethasone at a dose of 8 mg Q8h for up to 5 days. If still no improvement in symptoms, the patient may continue with the dexamethasone or consider switching to budesonide 9 mg QD. Refer to Section 7.1.2 for additional instructions on premedication with steroids.
 
 
Dose modifications for AL101:

Confidential

 Document State: Effective (Controlled)  
 CONFIDENTIAL

Page 56 of 118

Dose Modification Criteria for AL101 -Related Adverse Events	AL101 modification	
	Note: for any questions, please contact the Sponsor's Medical Monitor.	
	Cohort 1 (4 mg QW IV)	Cohort 2 (6 mg QW IV)
	
Interrupt AL101 until resolution to <math>\leq</math> Grade 1 (refer to Section 6.6.2 and above for management guidelines for diarrhea).
 
Decrease AL101 dose to 2.4 mg QW.
 
If the diarrhea does not resolve to Grade 1 by 14 days, the patient will be discontinued from AL101 (refer to Section 4.5 for early withdrawal of patients from therapy or assessment).
 
If treatment interruption is longer than 28 days, the patient will be discontinued from AL101 (refer to Section 4.5 for early withdrawal of patients from therapy or assessment).
	
Interrupt AL101 until resolution to <math>\leq</math> Grade 1 (refer to Section 7.1.2 and above for management guidelines for diarrhea).
 
Change dose regimen to 6 mg 2 weeks on / 1 week off for the first episode.
 
Decrease AL101 dose to 4 mg QW for second episode and to 2.4 mg QW for third episode
 
If the diarrhea does not resolve to Grade 1 by 14 days, the patient will be discontinued from AL101 (refer to Section 4.5 for early withdrawal of patients from therapy or assessment).
 
If treatment interruption is longer than 28 days, the patient will be discontinued from AL101 (refer to Section 4.5 for early withdrawal of patients from therapy or assessment).

Grade 4 diarrhea	
Guidelines for the management of diarrhea:
 
 
• Evaluate patient carefully including laboratory assessments (chemistry, liver function tests and lipase)
 
• Loperamide 4 mg at the first onset of diarrhea, then 2 mg every 2 hours around-the-clock until diarrhea free for at least 12 hours. Patients may take loperamide 4 mg every 4 hours during the night. These doses should not be used for more than 48 hours due to the risk of paralytic ileus.
 
	
Guidelines for the management of diarrhea:
 
 
• Evaluate patient carefully including laboratory assessments (chemistry, liver function tests and lipase)
 
• Loperamide 4 mg at the first onset of diarrhea, then 2 mg every 2 hours around-the-clock until diarrhea free for at least 12 hours. Patients may take loperamide 4 mg every 4 hours during the night. These doses should not be used for more than 48 hours due to the risk of paralytic ileus.
 
• For patients that cannot tolerate loperamide or do not get adequate relief with maximum doses,
 

Confidential

 Document State: Effective (Controlled)  
 CONFIDENTIAL

Page 57 of 118

Dose Modification Criteria for AL101 -Related Adverse Events	AL101 modification Note: for any questions, please contact the Sponsor's Medical Monitor.	
	Cohort 1 (4 mg QW IV)	Cohort 2 (6 mg QW IV)
	
 
For patients that cannot tolerate loperamide or do not get adequate relief with maximum doses, standard doses of LOMOTIL® (diphenoxylate/atropine) may be added or used instead of loperamide.
 
Additional antidiarrheal measures, such as octreotide, may be used at the discretion of the investigator or treating physician
 
Treat with dexamethasone at a dose of 8 mg every Q8h for up to 5 days. If still no improvement in symptoms, the patient may continue with the dexamethasone or consider switching to budesonide 9 mg QD. Refer to Section 7.1.2 for additional instructions on premedication with steroids.
 
 
If the above measures have not worked, or patient has progressed to Grade 4, consult GI as necessary to evaluate for colitis.
 
Dose modifications for AL101:
 
Permanently discontinue AL101 (refer to Section 4.5 for early withdrawal of patients from therapy or assessment).
	
standard doses of LOMOTIL® (diphenoxylate/atropine) may be added or used instead of loperamide.
 
 
Additional antidiarrheal measures, such as octreotide, may be used at the discretion of the investigator or treating physician
 
Treat with dexamethasone at a dose of 8 mg Q8h for up to 5 days. If still no improvement in symptoms, the patient may continue with the dexamethasone or consider switching to budesonide 9 mg QD. Refer to Section 7.1.2 for additional instructions on premedication with steroids.
 
 
If the above measures have not worked, or patient has progressed to Grade 4, consult GI as necessary to evaluate for colitis.
 
Dose modifications for AL101:
 
Permanently discontinue AL101 (refer to Section 4.5 for early withdrawal of patients from therapy or assessment).

Diagnosed or suspected clinically significant gastrointestinal (GI) bleeding or unexplained drop in hemoglobin	
Interrupt AL101, perform appropriate diagnosis and treatment.
 
If GI bleeding is considered related to AL101 reduce 1 dose level to 2.4 mg QW.
	
Interrupt AL101, perform appropriate diagnosis and treatment.
 
If GI bleeding is considered related to AL101, Decrease to 4 mg QW for first episode and to 2.4 mg QW for second episode 1 dose level.

Confidential

 Document State: Effective (Controlled)  
 CONFIDENTIAL

Page 58 of 118

Dose Modification Criteria for AL101 -Related Adverse Events	AL101 modification	
	Note: for any questions, please contact the Sponsor's Medical Monitor.	
	Cohort 1 (4 mg QW IV)	Cohort 2 (6 mg QW IV)
	
If colitis is suspected please refer to Section 8.4.2, Table 10 for management guidelines for colitis.
 
If treatment interruption is longer than 28 days, the patient will be discontinued from the study.
	
If colitis is suspected please refer to Section 8.4.2, Table 10 for management guidelines for colitis.
 
If treatment interruption is longer than 28 days, the patient will be discontinued from the study.

Grade 3 or 4 gastric hemorrhage	
Permanently discontinue AL101 (refer to Section 4.5 for early withdrawal of patients from therapy or assessment).
	
Permanently discontinue AL101 (refer to Section 4.5 for early withdrawal of patients from therapy or assessment).

QTcF > 500 msec confirmed by at least one repeat ECG and at least 50 msec above baseline	
Interrupt if needed to optimize electrolyte management. If persists after electrolyte optimization (including dose modification of AL101 if necessary), discontinue.
 
If treatment interruption is longer than 28 days, the patient will be discontinued from the study.
	
Interrupt if needed to optimize electrolyte management. If persists after electrolyte optimization (including dose modification of AL101 if necessary), discontinue.
 
If treatment interruption is longer than 28 days, the patient will be discontinued from the study.

AST or ALT > 5 times the institutional ULN	
Interrupt AL101 until resolution to <math>\leq</math> Grade 1 and then resume at 1 dose level lower (i.e., 2.4 mg QW). Refer to Section 8.4.1 for hepatic function abnormalities and Section 8.4.5 for drug-induced liver toxicity management.
 
If treatment interruption is longer than 28 days, the patient will be discontinued from the study.
	
Interrupt AL101 until resolution to <math>\leq</math> Grade 1 and then decrease dose to 4 mg QW for first episode and to 2.4 mg QW for second episode.
 
Refer to Section 8.4.1 for hepatic function abnormalities and Section 8.4.5 for drug-induced liver toxicity management.
 
If treatment interruption is longer than 28 days, the patient will be discontinued from the study.

Hy's law cases (e.g. drug induced liver injury; DILI) as defined in Section 8.4.1 and assessed by the Investigator and Sponsor	
Immediately discontinue (refer to Section 4.5 for early withdrawal of patients from therapy or assessment).
	
Immediately discontinue (refer to Section 4.5 for early withdrawal of patients from therapy or assessment).

Confidential

 Document State: Effective (Controlled)  
 CONFIDENTIAL

Page 59 of 118

Dose Modification Criteria for AL101 -Related Adverse Events	AL101 modification	
	Note: for any questions, please contact the Sponsor's Medical Monitor.	
	Cohort 1 (4 mg QW IV)	Cohort 2 (6 mg QW IV)
Triglyceride Grade 3 elevations that persist after 4 weeks of medical management	Interrupt AL101 until resolution to $\leq$ Grade 1 and then resume at 1 dose level lower (i.e., 2.4 mg QW). If treatment interruption is longer than 28 days, the patient will be discontinued from the study.	Interrupt AL101 until resolution to $\leq$ Grade 1 and then decrease dose to 4 mg QW for first episode and to 2.4 mg QW for second episode. If treatment interruption is longer than 28 days, the patient will be discontinued from the study.
Grade 2 infusion-related reaction	Before next dose, premedicate with H1- and H2-blockers (diphenhydramine and ranitidine or equivalents) or dexamethasone (Refer to Section 7.1.2 for additional instructions on premedication with steroids). Refer to Section 6.6.1 for management of infusion-related reaction.	Before next dose, premedicate with H1- and H2-blockers (diphenhydramine and ranitidine or equivalents) or dexamethasone (Refer to Section 7.1.2 for additional instructions on premedication with steroids). Refer to Section 6.6.1 for management of infusion-related reaction.
$\geq$ Grade 3 infusion-related reaction	Interrupt AL101 (refer to Section 6.6.1 for management of infusion-related reaction). If treatment interruption is longer than 28 days, the patient will be discontinued from the study.	Interrupt AL101 (refer to Section 6.6.1 for management of infusion-related reaction). If treatment interruption is longer than 28 days, the patient will be discontinued from the study.
Any other AL101-related Grade 3 nonhematologic adverse event except electrolyte abnormalities that may be managed with supplements	Interrupt AL101 until resolution to $\leq$ Grade 1 and then resume at 1 dose level lower (i.e., 2.4 mg QW). If treatment interruption is longer than 28 days, the patient will be discontinued from the study (refer to Section 4.5 for early withdrawal of patients from therapy or assessment).	Interrupt AL101 until resolution to $\leq$ Grade 1 and then change dose regimen to 6 mg 2 weeks on / 1 week off for the first episode. Decrease dose to 4 mg QW for second episode and to 2.4 mg QW for third episode. If treatment interruption is longer than 28 days, the patient will be discontinued from the study (refer to Section 4.5 for early withdrawal of patients from therapy or assessment).

Confidential

 Document State: Effective (Controlled)  
 CONFIDENTIAL

Page 60 of 118

Dose Modification Criteria for AL101 -Related Adverse Events	AL101 modification	
	Note: for any questions, please contact the Sponsor's Medical Monitor.	
	Cohort 1 (4 mg QW IV)	Cohort 2 (6 mg QW IV)
Grade 4 non-hematologic AEs including Grade 4 non-hematologic lab abnormalities lasting > 72 hours	Permanently discontinue from IP (refer to Section 4.5 for early withdrawal of patients from therapy or assessment ).	Permanently discontinue from IP (refer to Section 4.5 for early withdrawal of patients from therapy or assessment ).

Confidential

 Document State: Effective (Controlled)  
 CONFIDENTIAL

Page 61 of 118

